16.2.4 Safety Analyses

Evaluation of the safety and tolerability of oral nafithromycin for 3 or 5 days in the treatment of CABP is an important primary objective for this Phase II study. Safety will be analyzed in the Safety Population ([Section 16.1.1](#)). Subjects in the Safety Population will be analyzed according to the treatment actually received.

Safety will be evaluated by presenting summaries of AEs, physical examinations, vital signs, laboratory evaluations (hematology evaluation, chemistry panel, UA, and ECG parameters). For each safety parameter, the last assessment made prior to the first administration of study drug will be used as the baseline value for all analyses.

The incidence of TEAEs (defined in [Section 14.1.1](#)) will be presented by system organ class and preferred term according to MedDRA®, by relationship to the administration of study drug, and by severity. In addition, the incidence of SAEs and AEs leading to discontinuation of study drug will be presented by system organ class, preferred term, and relationship to study drug. If the incidence of SAEs and AEs leading to discontinuation of study drug is low, only a listing will be provided.

Descriptive statistics of vital signs at each time point measured, as well as the change from baseline and PCS changes, will be presented. Descriptive statistics for ECGs and physical examinations will also be presented for each time point measured. The number and percentage of subjects with a normal physical exam result at baseline and an abnormal physical examination result at a follow-up assessment will be provided for each time point. Descriptive statistics for clinical laboratory tests and vital signs and for the change from baseline will be presented by study visit. Potentially clinically significant clinical laboratory results will be determined based on normal limits and percent change from baseline.

16.2.5 Pharmacokinetic Analyses

See [Section 15.0](#).

16.3 INTERIM ANALYSIS

No interim analysis is planned for this study.

16.4 HANDLING OF DROPOUTS AND MISSING DATA

Every effort will be made to collect all data at specified times. A detailed description of the handling of dropouts and missing data for all efficacy and safety evaluations will be provided in the SAP.

17.0 INVESTIGATOR REQUIREMENTS

17.1 PROTOCOL ADHERENCE

Each Investigator must adhere to the protocol as detailed in this document and agree that the Sponsor or Sponsor representative must approve any change to the protocol before seeking approval from the relevant ethics committee(s) and regulatory agency(ies). Each Investigator will be responsible for enrolling only those subjects who have met the protocol inclusion and exclusion criteria.

17.2 ELECTRONIC CASE REPORT FORMS AND DATA CAPTURE SYSTEM

Data collection will involve the use of an Electronic Data Capture (EDC) system, to which only authorized personnel will have access. Electronic case report forms will be used to capture study data in an EDC system. Entering of eCRFs should be handled in accordance with instructions from the Sponsor or Sponsor representative. All eCRFs must be completed by qualified study center personnel. Each Investigator is responsible for ensuring that accurate data are entered into the EDC system in a timely manner.

Before the first subject is dosed at the investigational site, the Sponsor or Sponsor representative will meet with the Investigator and the study center's personnel to train them on recording the data on the eCRFs using the EDC system. The Investigator or designee will be responsible for reviewing eCRFs, resolving data queries generated by the Sponsor via the system, providing missing or corrected data, approving all changes performed on the subject data, and endorsing these data within the EDC system. This approval method will include applying an electronic signature, a uniquely assigned user name, and a password that together will represent a traditional handwritten signature.

Queries may be issued electronically to the clinical study center and answered electronically by that study center's personnel. The identifying information (assigned user name, date, and time) for both the originator of the query and the originator of the data change (if applicable) will be collected.

All data collected in the context of this study will be stored and evaluated per regulatory requirements and applicable guidance for electronic records.

17.3 SOURCE DOCUMENT MAINTENANCE

Source documents may include, but are not limited to, study progress notes, study- or subject-specific e-mail correspondence, computer printouts, laboratory data, and recorded data from automated instruments, study drug accountability records. The original signed ICF for each participating subject shall be filed with records kept by the Investigator. All documents produced in this study will be maintained by the Investigator and made available for inspection by the Sponsor or Sponsor representative and applicable regulatory authorities.

17.4 STUDY MONITORING REQUIREMENTS

The Sponsor or Sponsor representative will conduct center visits to inspect study data, subjects' medical records, and eCRFs in accordance with current ICH E6 Good Clinical Practice (GCP) guideline, and the respective US, EU and local regulations and guidelines, as applicable. The Sponsor or Sponsor representative will also be able to review query status remotely, which may warrant additional communication with the Investigator and the study center's personnel. The Investigator will make available to the Sponsor, or Sponsor representative, source documents, signed ICFs, and all other study-related documents.

The Investigator will allow the Sponsor or Sponsor representative and applicable regulatory authorities to inspect facilities and records relevant to this study.

17.5 STUDY COMPLETION

The Sponsor requires the following data and materials before the study can be considered complete or terminated:

- Clinical and laboratory results from Screening through TOC
- eCRFs properly completed by appropriate study personnel and signed and dated by the Investigator within the EDC system. This approval method will include applying an electronic signature, a uniquely assigned user name, and a password that together will represent a traditional handwritten signature
- Copies of complete study drug accountability records (e.g., study drug inventory logs and shipment and return records)
- Copies of all relevant ethics committee(s) and regulatory agency(ies) approvals and acknowledgements
- A summary of the study prepared by the Investigator (an ethics committee or regulatory agency summary letter is acceptable)

18.0 PROTECTION OF HUMAN SUBJECTS AND GENERAL STUDY ADMINISTRATION

18.1 STATEMENT OF COMPLIANCE

This study will be conducted in compliance with the current ICH E6 GCP guideline, the ethical principles of the Declaration of Helsinki, current FDA, European Union clinical trials related guidelines, and any additional relevant ethics committee or regulatory agency-required procedures, whichever represents the greater protection for the individual.

Investigators will apply due diligence to avoid protocol deviations. No authorized deviations or protocol waivers will be permitted. All significant protocol deviations will be recorded and reported in the clinical study report.

18.2 SUBJECT CONFIDENTIALITY

The Sponsor, its designee, the Investigator and all parties involved will comply with applicable subject data privacy regulations/guidance as per international and local requirements. The Investigator must assure that the privacy of the subjects, including their identity and all personal medical information, will be maintained at all times. In eCRFs and other documents or image material submitted to the Sponsor, subjects will be identified not by their names, but by an identification code (e.g., initials and identification number).

Personal medical information may be reviewed for the purpose of subject safety and/or verifying data in the source and transcribed onto the eCRF. This review may be conducted by the study monitor, properly authorized persons on behalf of the Sponsor, the quality assurance unit, and/or regulatory authorities. Personal medical information will always be treated as confidential.

18.3 INFORMED CONSENT

This study will be conducted in compliance with the current ICH E6 GCP guideline pertaining to informed consent, the current US CFR (Title 21, Parts 50 Subparts B and D, 56 and 312) as well as relevant European and local guidelines. Subjects will give written consent to participate in the study at the first visit, before initiation of any study-related procedures, after having been informed about the nature and purpose of the study, participation and termination conditions, risks, and benefits. If a subject is unable to provide written informed consent, the subject's legally acceptable representative(s) may provide written consent, as approved according to institution specific guidelines. The ICF must be signed and dated by the subject, or the subject's legally authorized representative(s), before study participation. An original copy of the signed ICF must be provided to the subject or legally acceptable representative(s). If applicable, the ICF will be provided in certified translation (native language) for non-English-speaking subjects. Signed ICFs must remain in the subjects' study files and be available for verification by the Sponsor or Sponsor representative at any time.

18.4 ETHICS COMMITTEE APPROVAL

The relevant ethics committee(s) and regulatory agency(ies) must approve the protocol or amended protocol (if applicable) and the corresponding ICF before the study may be initiated as per local requirements; any recruiting materials before use; and subsequent amended protocols and corresponding ICFs, before instituting amendment-specified changes to the study, unless required for subject safety following the local legislation.

The Investigator is responsible for informing the relevant ethics committees and regulatory authorities of any changes made to the protocol, and to advise the relevant ethics committees and regulatory authorities, at least once a year, about the progress of the study. The Investigator (or Sponsor, if applicable) is also responsible for notifying the relevant ethics committees and regulatory authorities of any significant AEs that occur during the study according to local ethics committee requirements.

19.0 DATA HANDLING AND RECORD KEEPING

Training sessions, regular monitoring of the investigative center by the Sponsor or Sponsor representative, instruction manuals, and data verification, crosschecking, and auditing will be provided or performed to ensure quality of all study data. One or more Investigator meetings will be held to prepare the Investigator and other study personnel for appropriate collection of study data.

The Sponsor or Sponsor representative will review and validate study data as defined in the monitoring plan.

It will be the responsibility of the Investigator to ensure that the essential documents are available in the Investigator's files or at the institutional center. Any or all of these documents should be available for monitoring by the Sponsor or Sponsor representative and inspection by the regulatory authorities as defined in the monitoring plan.

19.1 STUDY DRUG ACCOUNTABILITY

It is the responsibility of the Investigator or designee to ensure that current records of study drug inventory and accountability are maintained. Records must be readily available for inspection by the Sponsor or Sponsor's Representative and open to inspection at any time by applicable regulatory authorities.

19.2 RETENTION AND REVIEW OF RECORDS

Records and documents pertaining to the conduct of this study in all formats (including, but not limited to, written, electronic, magnetic, and optical records and scans/X-rays) must be retained by the Investigator for a period of at least 15 years after study completion unless local regulations or institutional policies require a longer retention period or otherwise notified in writing by the Sponsor. These records include CRFs, source documents, ICFs, regulatory documents, clinical reports and laboratory results (including, but not limited to, all local and central laboratory and microbiology results), and medication inventory records.

No study records shall be destroyed without notifying the Sponsor and providing the Sponsor the opportunity to arrange long-term storage for such study records or authorizing in writing the destruction of these records after the required retention period.

The Investigator must permit access to any documentation relating to the study upon request of the Sponsor or Sponsor representative, the corresponding relevant ethics committee(s) or regulatory agency(ies). If the Investigator for the study retires, relocates, or for other reasons withdraws from the responsibility of keeping study records, custody must be transferred to a suitable alternate custodian employee of the institution or to a suitably qualified and responsible third party. The Sponsor must be notified in writing of the name and address of the new custodian in advance of the transfer.

The Investigator agrees by his or her participation that the results of this study may be used for submission to national or international registration. If required, these authorities will be provided with the name of the Investigator and his or her address, qualifications, and extent of involvement.

Data generated by this study must be available for inspection by applicable regulatory authorities, the Sponsor or Sponsor representative, and the relevant ethics committee(s) and regulatory agency(ies) as appropriate. At the request of a subject's parent(s) or legally acceptable representative(s), medical information may be given to the subject's personal physician or other appropriate medical personnel responsible for the subject's welfare.

19.3 DECLARATION OF THE END OF STUDY AND CLINICAL STUDY REPORT

For clinical investigational centers located in the EU, a declaration of the end of the clinical study will be made according to the procedures outlined in Directive 2001/20/ED, Article 10(c); for other countries, local regulations will be followed.

Last subject last visit is defined as completion of the FU visit for the final subject enrolled in the study. This will be considered the end of the trial for global clinical trial submission.

Whether the study is completed or prematurely terminated, the Sponsor will ensure that the clinical study reports are prepared and provided to the regulatory authority(ies) as required by the applicable regulatory requirement(s). The Sponsor will also ensure that the clinical study reports in marketing applications meet the standards of the ICH Harmonised Tripartite Guideline E3: Structure and Content of Clinical Study Reports. Where required by applicable regulatory requirements, an Investigator signatory will be identified for the approval of the clinical study report. Upon completion of the clinical study report, the Sponsor will provide the Investigators with the full summary of the study results. The study results summary will also be made publicly available according to applicable FDA/EU requirements.

20.0 FINANCING AND INSURANCE

The financing and insurance for this study are outlined in the Clinical Trial Agreement.

APPENDIX I ALLOWED AND DISALLOWED PRIOR ANTIBIOTICS

Allowed Antibiotics (One dose within 72 h prior to randomization*)	Disallowed Antibiotics
Penicillins	
Amoxicillin Amoxicillin-Clavulanate Amoxicillin-Sulbactam Ampicillin Ampicillin-Sulbactam Dicloxacillin	Nafcillin Oxacillin Penicillin-G or -V Piperacillin Piperacillin-Tazobactam Ticarcillin-Clavulanate Benzathine/Penicillin-G Procaine
Cephalosporins	
Cefaclor Cefadroxil Cefazolin Cefdinir Cefepime Cefixime (200 mg) Cefditoren Cefotaxime	Cefpodoxime Cefprozil Ceftaroline Ceftazidime Ceftibuten Cefuroxime Cephalexin Loracarbef Cefixime (400 mg) Ceftriaxone
Carbapenems	
Doripenem Imipenem Meropenem	Ertapenem
Glycopeptides	
Televancin Vancomycin	Dalbavancin Oritavancin
Fluoroquinolones	
Ciprofloxacin	Levofloxacin Moxifloxacin
Macrolides	
Clarithromycin Erythromycin	Azithromycin Clarithromycin XL
Tetracyclines	
Doxycycline (100 mg) Minocycline	Doxycycline (200 mg) Minocycline Extended Release Tigecycline
Oxazolidinones	
Linezolid	Tedizolid
Miscellaneous	
Clindamycin Metronidazole Trimethoprim-sulfamethoxazole/Co-trimoxazole	

*Prior (within 72 h prior to randomization) administration of potentially effective systemic antibacterial therapy is an Exclusion Criterion ([Section 9.3](#)); however, subjects may be eligible for the study despite prior antimicrobial therapy if they received a single dose of a single short-acting systemic antibiotic within 72 h prior to randomization. For the purposes of this protocol, short-acting is defined as having a dosage frequency of more than once a day. If a subject received a prior short-acting systemic antibiotic that is not listed here, the Investigator must contact the Medical Monitor to ensure subject eligibility.

APPENDIX II PORT SCORE CALCULATION

Subject Characteristic	Point Assignment
Age	
Male	Age (years)
Female	Age (years) -10
Nursing home resident ¹	+10
Coexisting illnesses	
Neoplastic disease ²	+30
Liver disease ³	+20
Congestive heart failure ⁴	+10
Cerebrovascular disease ⁵	+10
Renal disease ⁶	+10
Physical-examination findings	
Altered mental status ⁷	+20
Respiratory rate ≥ 30 /minute	+20
Systolic blood pressure < 90 mm Hg	+20
Temperature $< 35^{\circ}\text{C}$ (95°F) or $\geq 40^{\circ}\text{C}$ (104°F)	+15
Pulse ≥ 125 /minute	+10
Laboratory and radiographic findings	
Arterial pH < 7.35 ⁸	+30
Blood urea nitrogen ≥ 30 mg/dL (11 mmol/L) ⁶	+20
Sodium < 130 mmol/L	+20
Glucose ≥ 250 mg/dL (14 mmol/L)	+10
Hematocrit $< 30\%$	+10
Partial pressure of arterial oxygen < 60 mm Hg or oxygen saturation $< 90\%$ (by pulse oximetry) ⁸	+10
Pleural effusion	+10
PORT Score	Sum of numbers above

PORT Risk Class	PORT Score
I (ineligible for study)	0-50
II (eligible)	51-70
III (eligible)	71-90
IV (score of 91-105 eligible and 106-130 ineligible)	91-130
V (ineligible for study)	≥ 131

- Subjects that reside in a nursing home are excluded from the study and should not be enrolled per Exclusion Criterion #1.
- Neoplastic disease is defined as any cancer, except basal or squamous cell cancer of the skin that was active at the time of presentation or diagnosed within one year of presentation. Subjects with neoplastic lung disease are excluded from the study and should not be enrolled per Exclusion Criterion #7.
- Liver disease is defined as a clinical or histologic diagnosis of cirrhosis or another form of chronic liver disease, such as chronic active hepatitis. Subjects with liver test abnormalities or evidence of end-stage liver disease as defined in Exclusion Criterion #8 should not be enrolled.
- Congestive heart failure is defined as systolic or diastolic ventricular dysfunction documented by history, physical examination, and chest radiograph, echocardiogram, multiple gated acquisition scan,

- or left ventriculogram. Subjects with acute congestive heart failure are excluded from the study and should not be enrolled per Exclusion Criterion #11.
5. Cerebrovascular disease is defined as a clinical diagnosis of stroke or transient ischemic attack or stroke documented by magnetic resonance imaging or CT.
 6. Renal disease is defined as a history of chronic renal disease or abnormal blood urea nitrogen and creatinine concentrations documented in the medical record. Subjects with compromised renal function are excluded from the study and should not be enrolled per Exclusion Criterion #8.
 7. Altered mental status is defined as disorientation with respect to person, place, or time that is not known to be chronic, stupor, or coma.
 8. For subjects without an optional ABG at Screening, no points will be added for pH or PaO₂; however, oxygen saturation results should be used in place of PaO₂.

Reference: Fine, 1997.

APPENDIX III CABP SYMPTOM SEVERITY GUIDANCE FOR INVESTIGATOR ASSESSMENT

CABP Symptom	Absent	Mild	Moderate	Severe
Dyspnea (Shortness of Breath [SOB])	No CABP-associated SOB; or return to pre-CABP baseline SOB	SOB with only strenuous activity but it does not interfere with subject’s usual daily activities; or mild SOB above pre-CABP baseline	SOB with usual activities and it does interfere with some of the subject’s usual daily activities; or moderate SOB above pre-CABP baseline	SOB with minimal exertion or at rest and it limits most of the subject’s usual daily activities; or severe SOB above pre-CABP baseline
Cough	Resolution of cough; or return to pre-CABP baseline cough	Cough present, infrequent, and it does not interfere with subject’s usual daily activities; or mild cough above pre-CABP baseline	Cough present, frequent, and it does interfere with some of the subject’s usual daily activities; or mild cough above pre-CABP baseline	Cough is present throughout the day and night; it limits most of the subjects’ usual daily activities and sleep patterns; or mild cough above pre-CABP baseline
Production of Purulent Sputum	No production of purulent sputum; or return to pre-CABP baseline productive cough	Production of small amount of purulent sputum; or minimal amount of sputum production above pre-CABP baseline	Production of moderate amount of purulent sputum; or moderate amount of sputum production above pre-CABP baseline	Production of large amount of purulent sputum; or large amount of sputum production above pre-CABP baseline
Pleuritic Chest Pain	No CABP-associated pleuritic chest pain	CABP-associated pleuritic chest pain present occasionally with deep breathing but it does not interfere with subject’s usual daily activities	CABP-associated pleuritic chest pain is present with normal breaths, and it does interfere with the subject’s usual daily activities	CABP-associated pleuritic chest pain is present at rest and/or with shallow breathing, and it limits most of the subject’s usual daily activities

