9.2 INCLUSION CRITERIA

Subjects are required to meet all of the following inclusion criteria:

1. Male or female ≥ 18 years of age
2. Willing to participate in the study and provide written informed consent before any protocol specific assessment is performed
3. Meet the following clinical criteria for CABP:
 - a. Have at least TWO of the following symptoms (new or worsening):
 - Dyspnea (shortness of breath)
 - Cough
 - Production of purulent sputum
 - Pleuritic chest pain
 - b. Have at least TWO of the following vital sign abnormalities:
 - Fever or hypothermia documented by the Investigator (oral, rectal, or tympanic temperature $> 38.0^{\circ}\text{C}$ [100.4°F] or $< 36.0^{\circ}\text{C}$ [95.5°F])
 - Hypotension, defined as systolic blood pressure < 90 mm Hg
 - Tachycardia, defined as heart rate > 90 beats per minute
 - Tachypnea, defined as respiratory rate > 20 breaths per minute
 - c. Have at least ONE of the following laboratory abnormalities:
 - Hypoxemia defined as arterial oxygen saturation $< 90\%$ by pulse oximetry or $\text{PaO}_2 < 60$ mm Hg by ABG
 - Auscultatory findings on pulmonary examination consistent with bacterial pneumonia or pulmonary consolidation (e.g., rales, dullness on percussion, bronchial breath sounds, or egophony)
 - Elevated total WBC count ($> 10,000$ cells/ mm^3) or leucopenia (WBC $< 4,000$ cells/ mm^3)
 - Elevated immature neutrophils ($> 15\%$ band forms), regardless of total peripheral WBC count
 - d. Radiographic evidence of CABP:

- Radiographically-confirmed pneumonia, i.e., new or progressive pulmonary infiltrate(s) on CXR or CT scan consistent with acute bacterial pneumonia within 48 h prior to randomization
- e. PORT score of 51 to 105 (PORT Risk Class of II, III or IV) ([Appendix II](#))

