- Record vital signs of body temperature (oral, rectal, or tympanic), blood pressure, heart rate, respiratory rate, and pulse oximetry; the highest daily temperature should be recorded, and attempts should be made to measure temperatures using the same methodology throughout the study
- Perform a complete physical examination, including general appearance, skin, eyes, ears, nose, throat, lungs, heart, abdomen, back, extremities, lymph nodes, vascular, and neurological exams
- Assess CABP symptom severity ([Appendix III](#))
- Obtain a 12-lead ECG
- Identify, assess and record any AEs (since the time of informed consent)

Radiographic Evaluation

- Obtain a CXR or chest CT scan for all subjects at Screening. If a CXR is performed, anteroposterior and lateral views are preferred, and confirmation of new or progressive pulmonary infiltrates consistent with CABP may occur with either (or both) CXR view; however, posteroanterior (i.e., portable) views are also acceptable. Chest radiography may be obtained as part of routine, non-study evaluation of a subject presenting with signs and symptoms of CABP and therefore may be performed in some circumstances before informed consent is obtained for participation in this study; radiological evaluations already performed as part of the subject's regular medical care or site's standards of care within 48 h before randomization do not have to be repeated to determine subject eligibility. Radiologic evaluation(s) will be performed locally and interpreted by appropriately qualified personnel who are certified or licensed to interpret chest radiographs according to applicable regional requirements, and the evaluations will be reviewed by the Investigator or qualified personnel during the Screening Visit; the conclusions of the Investigator's review will be the basis for subject inclusion. The written radiography report (i.e., formal interpretation of the radiographic image or film) should be included in the source documents; however, the radiography images or films are not needed in the source documents.

Local or Regional Laboratory Assessments for Study Eligibility:

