13.2 CLINICAL OUTCOME ASSESSMENTS

13.2.1 Clinical Response at Day 4

The primary efficacy endpoint is clinical response (response, non-response, or indeterminate) at Day 4, tested in the ITT Population. Clinical response (response, non-response, or indeterminate) at Day 4 will also be tested in the micro-ITT Population as a secondary efficacy endpoint. Clinical response is determined programmatically using the Investigator's determination of CABP symptoms entered into the eCRF ([Table 13.2.1-1](#)). The Investigator is not responsible for categorizing subjects as clinical response, non-response, or indeterminate at Day 4. The severity of the subject CABP symptoms of dyspnea (shortness of breath), cough, production of purulent sputum, and pleuritic chest pain will be evaluated on a 4-point scale (absent, mild, moderate, or severe) based upon the CABP Symptom Severity Guidance in [Appendix III](#).

Table 13.2.1.-1. Clinical Outcome Assessment at Day 4.

Outcome	Definition
Clinical Response	Alive and programmatically-determined improvement of at least 1 level (e.g., severe to moderate, moderate to mild, mild to absent) in at least 2 CABP symptoms (dyspnea, cough, production of purulent sputum, and pleuritic chest pain) compared to Screening, without worsening in any other symptom. Severity of symptoms is based on a 4-point scale (absent, mild, moderate, or severe) (Appendix III).
Clinical Non-Response	Meets any of the following criteria: 
 • No programmatically-determined improvement of at least 1 level in at least 2 CABP symptoms compared to Screening

Table 13.2.1.-1. Clinical Outcome Assessment at Day 4.

Outcome	Definition
	
 Worsening in any of the 4 CABP symptoms compared to Screening Requires alternative rescue antibacterial therapy for CABP prior to Day 4 Death from any cause prior to Day 4
Indeterminate	Study data are missing for evaluation of efficacy at Day 4 for any reason, including lost to follow-up.

Abbreviations: CABP = community-acquired bacterial pneumonia.

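### Appendix III lets a subject with pre-existing dyspnea be graded in absolute terms or against the pre-CABP level, with no rule on which, so the Day 4 result can depend on the clause chosen.

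*Combined protocol and SAP*

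**What the plan says.** Section 13.2.1 derives clinical response by program from the investigator's grades of four symptoms. A responder improves by at least one level from Screening in at least two symptoms, with none worse. Table 13.2.1-1 lists as a ground for non-response "Worsening in any of the 4 CABP symptoms compared to Screening".

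The grades come from Appendix III. In the dyspnea row:

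- Absent is "No CABP-associated SOB; or return to pre-CABP baseline SOB". Both parts refer to the pneumonia or to the state before it.
- Mild, Moderate and Severe each pair an absolute description with a relative one, joined by a plain or. Severe, for instance, opens with "SOB with minimal exertion or at rest and it" limits most usual activities. The relative alternatives are stepped, for example "mild SOB above pre-CABP baseline" and then "moderate SOB above pre-CABP baseline".

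The appendix and Section 13.2.1 state no precedence between the two and no requirement to keep to one across visits.

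Inclusion Criterion 3a (Section 9.2) reads "Have at least TWO of the following symptoms (new or worsening", so a worsened chronic symptom qualifies. At Screening, Section 11.1 asks for a medical history of conditions and then says "Assess CABP symptom severity", meaning current severity. Neither that section nor Table 3-1 with its footnotes lists the symptom level before CABP.

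**The concern.** The two kinds of clause agree when the subject had no dyspnea before the pneumonia. They can disagree when some was already present. Sites may then choose differently, or one site may choose differently at Screening and at Day 4, and all would be following the appendix.

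The endpoint has little slack. Criterion 3a requires only two symptoms, so a subject who enters with exactly two must improve in both. One grade that reads unchanged makes that subject a non-responder, and one that reads worsened does so for any subject. Because classification is programmed from the grades, the analysts cannot repair inconsistent grading later. The same grades also feed Day 4 response in the micro-ITT population and the Day 4 endpoint that combines symptoms with vital signs (Section 13.2.3).

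What is at stake is the accuracy of the per-arm Day 4 rates, which Section 16.2.1 says should inform later studies. The interval around each rate does not reflect a shift caused by the definition.

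**Working it through.** **The plan's own figure.** Inputs from Sections 16.2.1 and 16.2.3.1: response rate 78%, n = 75 per arm, Clopper-Pearson 95% interval. With x = 0.78 × 75 = 58.5, the lower limit is the 2.5% quantile of Beta(58.5, 17.5) = 66.94%. The upper limit is the 97.5% quantile of Beta(59.5, 16.5) = 86.75%. The plan states 66.9% to 86.7%, so it is reproduced. The arithmetic is not at fault; the question is what counts as a response.

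**Course 1: still above the earlier level at Day 4.** Before CABP the subject is short of breath with usual activities. At Screening the subject is breathless on minimal exertion, moderately above the earlier level. At Day 4 the subject is better and only mildly above the earlier level, but still breathless on minimal exertion.

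| Clause at Screening | Clause at Day 4 | Grades | Scored as |
|---|---|---|---|
| relative | relative | Moderate to Mild | improved |
| absolute | absolute | Severe to Severe | unchanged |
| absolute | relative | Severe to Mild | improved |
| relative | absolute | Moderate to Severe | worsened |

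**Course 2: no clinical change.** At both visits the subject is short of breath with usual activities, mildly above the earlier level.

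| Clause at Screening | Clause at Day 4 | Grades | Scored as |
|---|---|---|---|
| relative | relative | Mild to Mild | unchanged |
| absolute | absolute | Moderate to Moderate | unchanged |
| absolute | relative | Moderate to Mild | improved (false) |
| relative | absolute | Mild to Moderate | worsened (false) |

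**What this shows.** Each clause, used alone, rises and falls with the subject's true state. Consistent use of one clause therefore cannot give opposite directions for the same course; it can give improved against unchanged, as in the first two lines of course 1. A false improvement or worsening needs a switch between visits.

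**From grade to endpoint.** Suppose the course 1 subject entered with dyspnea and cough only, and cough improved by one level. Relative clauses throughout give two improved symptoms and none worse: response. Absolute clauses throughout give one improved symptom: non-response. If two other symptoms had improved, unchanged dyspnea would not matter, but worsened dyspnea still would.

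**Size.** One subject reclassified is 1/75 = 1.3 percentage points of an arm. The share with pre-existing dyspnea is not in the documents. Assuming 5% to 30%, about 4 to 22 subjects per arm, a ceiling follows if every one were a responder turned into a non-responder: (58.5 − 4)/75 = 72.7% down to (58.5 − 22)/75 = 48.7%. This is a bound and not an estimate. Many affected subjects would have the same result under either clause, and changes in both directions partly cancel.

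**The case against.** The strongest reply is that the appendix is meant to be read as CABP-attributable severity. The column is headed as CABP symptoms, and both parts of Absent refer to CABP. A sensible investigator would use the relative clauses for a chronically breathless subject. This stands in part, and it limits the point. A reader might infer that a subject who is fully back to the earlier level at Day 4 can also score improved, unchanged or worsened. The documents do not support that: the Absent cell fits this subject expressly, and any grade above Absent at Screening then gives an improvement. The reply does not settle the subject who is still above the earlier level, because the absolute clauses in Mild to Severe remain available and nothing ranks them.

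Eligibility also narrows the group. A reader might infer that severe COPD is the only chronic lung disease removed. Exclusion 7 also removes bronchiectasis, bronchial obstruction, neoplastic lung disease and neurological disorders that prevent clearance of secretions. Exclusion 11 lists congestive heart failure, although note 4 of Appendix II describes the exclusion as acute failure. Less severe COPD can still enter, and Criterion 3a admits worsened symptoms.

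The rater need not change between visits. That is correct, but the protocol does not require the same rater either. Section 11.1 asks for a consistent method of measuring temperature and has no counterpart for symptom grades.

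Finally, the study is blinded and exploratory, with no formal comparison planned (Section 16.2), and site training and investigator meetings are foreseen (Sections 17.2 and 19.0). This lowers the stakes. The content of the training is not in the documents.

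**Conclusion.** The point holds for subjects with pre-existing dyspnea who are still above their earlier level at Day 4. For them the choice of clause can change improved to unchanged, and a switch of clause between visits can produce a false improvement or worsening. It is an avoidable source of misclassification in the primary endpoint and worth a cheap clarification.

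The size cannot be fixed from the documents beyond 1.3 points per subject reclassified in an arm of 75. A reader might be drawn to an estimate of 2 to 10 points, from 10% to 25% of subjects affected and 20% to 40% of those reclassified (0.10 × 0.20 = 2%; 0.25 × 0.40 = 10%). The documents give neither share, and the product counts every change in the same direction. With blinded grading the error should be mainly non-differential: it can shift each arm's rate and tends to dilute differences between arms. Nothing here shows a bias in favor of one arm.

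The conclusion rests on the protocol's text. The eCRF and the separate SAP promised in Section 16.2 were not available, so the absence of a recorded pre-CABP level is established only for the listed procedures and Table 3-1.

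**What to change.** State in Appendix III and Section 13.2.1 that, for dyspnea, cough or purulent sputum present before CABP, the clauses relative to the pre-CABP level apply at Screening and every later visit, with return to that level graded Absent. State that otherwise the absolute clauses apply at every visit. Leave the pleuritic chest pain row as it is, since it has no relative clause.

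Correct the cough row in the same change. Its relative clause says mild under Mild, Moderate and Severe alike, so the rule could not grade a chronic cough until the Moderate and Severe cells are stepped.

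If the eCRF does not already capture it, add one Screening item each for dyspnea, cough and sputum that records the level before CABP, and show it to the rater at later visits.

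The cost is a short rule in two places, two corrected cells, up to three eCRF fields and a little more history-taking. Visits, sample size and the analysis method do not change.
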